2.4.3 Clinical Efficacy in Neoadjuvant Setting

Karam et al. performed a single-institution, single-arm phase 2 clinical trial. Patients with locally advanced nonmetastatic biopsy-proven ccRCC were eligible. Patients received axitinib 5mg for up to 12 wk. Axitinib was continued until 36h prior to surgery. Patients underwent partial or radical nephrectomy after axitinib therapy.

The primary outcome was objective response rate prior to surgery. Secondary outcomes included safety, tolerability, and quality of life. A dedicated radiologist independently reviewed all computed tomography scans to evaluate for response using Response Evaluation Criteria in Solid Tumors (RECIST).

A total of 24 patients were treated. Twenty-two patients continued axitinib for 12 wk; 1 patient continued axitinib for 11 wk and underwent surgery as planned. One patient stopped treatment at 7 wk due to adverse events (AEs). Median reduction of primary renal tumor diameter was 28.3%. Eleven patients experienced a partial response per RECIST; 13 had stable disease. There was no progression of disease while on axitinib. The most common AEs were hypertension, fatigue, oral mucositis, hypothyroidism, and hand-foot syndrome. Postoperatively, 2 grade 3 and 13 grade 2 complications were noted. No grade 4 or 5 complications occurred. Functional Assessment of Cancer Therapy-Kidney Specific Index-15 changed over time, with quality of life worsening while on therapy, but by week 19, it was not statistically different from screening. Limitations include single-arm design and small patient numbers. The authors concluded that axitinib was clinically active and reasonably well tolerated in the neoadjuvant setting in patients with locally advanced nonmetastatic ccRCC, though larger studies are needed prior to further clinical use.¹⁹

3.0 REGISTRATION PROCEDURES

To enter eligible patients on study, investigators register patients by contacting the study research coordinator, [name] at [contact]. All patients will be registered in ONCORE. ONCORE will also act as the data management system. Please refer to the calendar for data collection details.

4. TREATMENT PLAN

Inclusion Criteria:

1. Localized clear cell renal carcinoma without evidence of distant metastases
2. Imperative indication for nephron sparing surgery
 - baseline CKD (stage 3, GFR <60 ml/min/1.73m²), **or** anatomically or functional solitary kidney (defined by renal scintigraphy of contralateral renal unit with <15% function) **or** bilateral synchronous disease); **and**
 - RENAL score ≥ 10 or proximity to renal hilum (defined as <2 mm away from at least 2 renal hilar vessels-the main artery/vein or first order branches); **and**
 - Radical nephrectomy would lead to severe CKD (stage 4, GFR <45 ml/min/1.73m²).²³
3. Male or female, age ≥ 18 years
4. Karnofsky performance status ≥ 70 %.
5. Adequate organ function as defined by:
 - a. Absolute neutrophil count (ANC) $\geq 1,000/\mu\text{L}$
 - b. Platelets $\geq 100,000/\mu\text{L}$
 - c. Hemoglobin ≥ 9.0 g/dL
 - d. Serum calcium ≤ 12.0 mg/dL
 - e. Serum creatinine ≤ 1.5 x ULN
 - f. Total serum bilirubin ≤ 1.5 x ULN
 - g. SGOT ≤ 2.5 x ULN and SGPT ≤ 2.5 x ULN
6. Signed informed consent and willingness/ability to comply with scheduled visits, treatment plans, laboratory tests, and other study procedures

Exclusion Criteria:

- 1) Presence of Metastatic Disease
- 2) Elective indication for nephron sparing surgery
- 3) Non-clear cell histology
- 4) Simple or intermediate renal mass on imaging (R.E.N.A.L score ≤ 9)
- 5) Prior systemic treatment of any kind or radiotherapy for RCC

- 6) NCI CTCAE Version 4.03 grade 3 hemorrhage within 4 weeks of starting the study treatment
- 7) Ongoing cardiac dysrhythmias of NCI CTCAE Version 4.03 grade ≥ 2 . Controlled atrial fibrillation is permitted.
- 8) Pregnancy or breastfeeding. Female subjects must be surgically sterile or be postmenopausal, or must agree to use effective contraception during the period of therapy. All female subjects with reproductive potential must have a negative pregnancy test (serum) prior to enrollment. Male subjects must be surgically sterile or must agree to use effective contraception during the period of therapy. The definition of effective contraception will be based on the judgment of the principal investigator or a designated associate.
- 9) Other severe acute or chronic medical or psychiatric condition or laboratory abnormality that may increase the risk associated with study participation or study drug administration, or may interfere with the interpretation of study results, and in the judgment of the investigator would make the subject inappropriate for entry into this study.
- 10) Uncontrolled HTN
- 11) HTN with need for 2 or more anti-hypertensives to control it at baseline (because there isn't room to add more antihypertensives if axitinib causes increased BP)
- 12) CHF since axitinib can cause CHF
- 13) Baseline abnormal thyroid function tests
- 14) subjects with arterial thrombotic events in the prior 12 months (axitinib has never been studied in this population)
- 15) subjects who have had venous thrombotic events in the prior 6 months (axitinib has never been studied in this population)

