Investigational Protocol

Proposed Title: “PADRES” (Prior Axitinib as a Determinant of Outcome of REnal Surgery)

Co-Principal Investigators: [name].¹
UCSD Moores Cancer Center
[name]
Mail Code: 0987
[name]
[contact]
[contact]
Email: [contact]

[name].
Cleveland Clinic Taussig Cancer Center
[name]
[name]
[contact]
[contact]
E-mail: [contact]

[name], PhD
Section of Urologic Oncology
Glickman Urological and Kidney Institute
[name]
[name]
[contact]
[contact]
[contact]

Co-Investigators:

[name]	(UCSD)
J. [name]	(UCSD)
[name]	(UCSD)
[name]	(UCSD)
[name]	(Cleveland Clinic)
[name]	(Cleveland Clinic)
[name], PhD	(Spectrum Health/Michigan State)
[name]	(Fox Chase Cancer Center)
[name]	(Netherlands Cancer Institute)
[name]	(MD Anderson)
[name]	(MD Anderson)
[name]	(UT Southwestern)
[name]	(Mayo Clinic)
[name]	(Mayo Clinic)

[name] (U Wisconsin)
[name] (NYU)
[name] (NYU)
[name] (Vanderbilt)
[name] (KU Leuven)
[name] (KU Leuven)

Statistician: [name], MS
Clinical and Translational Research Institute
UC San Diego Health
[name]
[name]
[contact]
Email: [contact]

Research Coordinator: [name], CCRC
Clinical Research Coordinator
UC San Diego Moores Cancer Center
Clinical Trials Office, Rm # 2011
[name]
[name]
[contact]
[contact]
[contact]
Email: [contact]

Responsible Data Manager: [name], MS
Database Program Manager
UC San Diego Health System-Department of Urology
[name]
Moores Cancer Center Office: 2032
[name]
[contact]
[contact]
Email: [contact]

Investigational Agent: Axitinib

Sponsor: University of California San Diego

Protocol Version Date: May 31, 2017

SCHEMA

A single arm phase II study of axitinib in patients with clear cell renal cell carcinoma (RCC) in patients with strong indications for partial nephrectomy (PN) for whom PN is not currently possible due to anatomic considerations and residual renal function concerns. Evaluation of tumor downsizing will be performed including changes of tumor complexity by nephrometry score (n=50 total).

Evaluation:

- 1) Cross Sectional Imaging (CT a/p, or MRI as indicated) to delineate renal mass and surrounding structures:

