- 2) Laboratory Determinations: urinalysis, serum creatinine-based estimation of GFR, nuclear renal scintigraphy if contralateral kidney present
- 3) Metastatic Evaluation: Chest CT; Bone scintigraphy or Head CT/MRI (as may be appropriate)
- 4) Biopsy to confirm Clear Cell RCC
- 5) Define tumor Complexity by R.E.N.A.L Nephrometry Score

Major Inclusion Criteria:

- 1) Imperative indication for nephron sparing surgery (preexisting CKD or solitary kidney/anatomically functionally solitary kidney or bilateral synchronous disease); and
- 2) complex renal lesion defined as RENAL score ≥ 10 or proximity to renal hilum, defined as < 2 mm away from at least 2 renal hilar vessels-the main artery/vein or first order branches); and
- 3) radical nephrectomy would place patient on dialysis or leave patient with severe CKD (> stage IIIb

Enrollment

Axitinib-5 mg po BID x 8 weeks (with titration to 7mg BID as tolerated at 4 weeks), then re-staging

Repeat SCr based-estimation of GFR
Baseline u/a and assess for preop proteinuria

Outcomes

- 1) Assessment of Tumor Response (CT or MRI) after completion of axitinib therapy
 - a) RECIST v1.1 response / change in maximal tumor diameter
 - b) Change in R.E.N.A.L. Nephrometry Score
- 2) Ability to perform Partial Nephrectomy after TKI therapy with Negative Margins
- 3) Functional issues: avoidance of dialysis and severe CKD (stage 4, GFR < 30 ml/min/1.73 m²)
- 4) Safety indices
 - a) avoidance of major Complications: Clavien ≥ 3
 - b) avoidance of need for multiple blood transfusion

TABLE OF CONTENTS

	Page
1. OBJECTIVES	3
2. BACKGROUND	4
3. REGISTRATION PROCEDURES	10
4. TREATMENT PLAN/SUPPORTIVE CARE	10
5. STUDY CALENDAR	13
6. DOSING DELAYS/DOSE MODIFICATIONS	14
7. ADVERSE EVENTS: REPORTING REQUIREMENTS	15
8. PHARMACEUTICAL INFORMATION	16
9. MEASUREMENT OF EFFECT	18
10. STATISTICAL CONSIDERATIONS	20
11. DATA REPORTING AND MONITORING REQUIREMENTS	21
12. REFERENCES	21
APPENDIX 1: Axitinib Guidance Document: Concomitant Medication	22

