1. OBJECTIVES

We hypothesize that pretreatment with axitinib will be safe and improve the feasibility of complex nephron sparing surgery in select patients with localized clear cell RCC and imperative indications for partial nephrectomy.

- 1 Primary objective: The primary objective of the study is to prospectively assess utility of axitinib in facilitation of partial nephrectomy where partial nephrectomy was not thought to be safe/possible in the setting of imperative indication for complex renal masses in renal cell cancer.**
- 2 Secondary objectives: To determine the safety, tumor diameter (per RECIST v1.1) volume change, surgical morbidity and renal functional outcomes following neoadjuvant axitinib for RCC.**

Anatomical/morphometric:

- a) tumor diameter/volume change,
- b) conversion of hilar to non-hilar tumors,
- c) reduction in RENAL morphometric score.

Functional Considerations:

- a) Requirement of acute dialysis
- b) Change in GFR
- c) Whether or not GFR crosses 30 threshold, or decline by GFR to >50% of baseline.

Safety indices:

- a) Incidence of Clavien >3 complications
- b) Avoidance of need for multiple blood transfusions

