5. STUDY CALENDAR

	≤ 4 weeks prior to dosing	Baseline	Day 14 (± 3 days)		Day 28 (± 3 days)	End of Cycle (Day 58 ± 3 days)	End of Treatment ¹
Informed Consent	X						
Vital Signs/ECOG	X	X	X		X	X	X
History / Physical	X	X	X		X	X	X
Hematology ²	X	X*	X		X	X	X
Chemistries ³	X	X*	X		X	X	X
Coagulation ⁴	X					X	
Pregnancy Test ⁵	X						
Urinalysis ⁶	X				X	X	X
Drug Related AE's		X	X		X	X	X
TSH, T3, T4	X					As clinically indicated	X
Axitinib**		X-----X					
Tumor Imaging ⁷	X				X	X	

* Cycle 1, day 1 labs need not be repeated if done within 14 days. ;** Nephrectomy will be performed ≥ 1 days after the last dose of Axitinib

Footnotes for Schedule of Events

1. End of Treatment/Withdrawal: These assessments will occur at least 30 days after nephrectomy date.
2. Hematology: CBC with differential, platelets
3. Blood Chemistry: Albumin, total bilirubin, bicarbonate, BUN, calcium, chloride, creatinine, glucose, magnesium, phosphorus, potassium, SGOT [AST], SGPT [ALT], sodium, ALP, LDH (baseline only).
4. Coagulation: PT/INR and PTT
5. Pregnancy Test: Serum or urine test must be performed for all women of childbearing potential.
6. Urinalysis: with 24 hour urine to ensure protein < 2 grams for anyone with 2+ or greater protein on urinalysis.
7. Tumor Imaging: CT or MRI scan of the chest, abdomen and pelvis (with IV contrast, if possible) to be performed to assess disease status at screening, prior to nephrectomy and whenever disease progression is suspected. CT or MRI scan of the chest is optional at day 28 based on symptoms or pre-enrollment findings. CNS and bone imaging needed only if clinical signs/symptoms are suggestive. Follow up imaging after nephrectomy at the discretion of the treating MD and not part of this protocol.

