9.2 Response Criteria

Response to axitinib will be measured according to 3 mechanisms:

1. Percent in reduction of longest diameter of tumor.
2. RECIST criteria-Tumor response to therapy will be assessed by CT/MRI during second cycle of treatment according to the Response Evaluation Criteria in Solid Tumors (RECIST) version 1.1.1.²⁴ Clinical response of primary tumor will be classified by treating physicians as complete response (CR), partial response (PR), stable disease (SD), and progressive disease (PD), where:
 - a) Complete Response (CR): Disappearance of all target lesions
 - b) Partial Response (PR): At least a 30% decrease in the sum of the longest diameter (LD) of target lesions, taking as reference the baseline sum LD
 - c) Progressive Disease (PD): At least a 20% increase in the sum of the LD of target lesions, taking as reference the smallest sum LD recorded since the treatment started or the appearance of one or more new lesions
 - d) Stable Disease (SD): Neither sufficient shrinkage to qualify for PR nor sufficient increase to qualify for PD, taking as reference the smallest sum LD since the treatment started
3. RENAL score-morphometric measure which has been correlated with oncological prognosis, surgical risk stratification and renal functional outcomes in addition to response to primary TKI.²⁰

	1pt	2pts	3 pts
(R)adius (maximal diameter in cm)	≤4	>4 but < 7	≥ 7
(E)xophytic/endophytic properties	≥ 50%	<50%	Entirely endophytic
(N)earness of the tumor to the collecting system or sinus (mm)	≥7	>4 but <7	≤4
(A)nterior/Posterior	No points given. Mass assigned a descriptor of a, p, or x		
(L)ocation relative to the polar lines* * suffix "h" assigned if the tumor touches the main renal artery or vein	Entirely above the upper or below the lower polar line	Lesion crosses polar line	>50% of mass is across polar line (a) or mass crosses the axial renal midline (b) or mass is entirely between the polar lines (c)

[figure not shown]
For difficult to qualify/document cases, the primary surgeon may seek confirmation of the surgical Co-PIs ([name]/[name]) to confirm the change between baseline and post Rx status.

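### The screening RENAL score that admits patients is also the only baseline for the RENAL-reduction endpoint, so with no control arm any reading error tilts the measured change modestly toward reduction

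*Protocol*

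**What the plan says.** The design is "A single arm phase II study of axitinib", so there is no concurrent control. The Schema's pre-enrolment evaluation includes the step "Define tumor Complexity by R.E.N.A.L Nephrometry Score".

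Section 4 then uses that score twice. Inclusion 2 accepts "RENAL score ≥ 10 or proximity to renal hilum", with the other imperative conditions. Exclusion 4 bars "Simple or intermediate renal mass on imaging (R.E.N.A.L score ≤ 9", with no exception for hilar tumours. The two conflict for a hilar tumour scoring 9 or less. If exclusion 4 governs, every enrolled patient scores 10 to 12, the top of the scale.

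The same score is an outcome. The Schema lists "Change in R.E.N.A.L. Nephrometry Score", section 1 lists "reduction in RENAL morphometric score" among the anatomical secondary objectives, and section 9.2 makes it the third of three response measures.

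Section 5 shows tumour imaging at screening but none in the Baseline column. Its imaging footnote says scans are "to be performed to assess disease status at screening, prior to nephrectomy and whenever disease progression is suspected". Section 9.2 lets the primary surgeon, in difficult cases, ask the surgical co-PIs "to confirm the change between baseline and post Rx status". No repeat, masked or central reading is described.

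**The concern.** When patients are admitted because a noisy measurement exceeds a threshold, the errors in the admitted measurements are positive on average. A later measurement has no such selection, so the difference is negative on average even if nothing changed. A control group would show the same drift and allow it to be subtracted, but this trial has none.

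Some reading error is to be expected from the protocol's own imaging rules. Section 9.1 allows slices up to 10 mm (5 mm reconstruction for spiral CT), while the nearness component in section 9.2 changes category at 4 and 7 mm. Section 9.2 also foresees cases that are hard to classify.

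At stake is how a secondary endpoint is interpreted. Section 2.3.3 presents the morphometric score as the study's objective measure of complexity, and section 2.3.2 cites a pazopanib trial in which 71% of tumours had a lower score after treatment. A reader may well compare the two. Part of any reduction seen here would come from how patients were selected.

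**Working it through.** The protocol states no expected RENAL change and no reader agreement, so there is no figure to reproduce. The direction follows from the text. The size needs assumptions.

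**Assumptions.** True score before selection: a rounded normal with mean 9 or 10.5 and SD 1.5, limited to 4–12. Each read equals the true score with probability *a* = 0.8 or 0.6; otherwise it is one point off, up or down with probability *q* = (1 − *a*)/2 each. A read above 12 is recorded as 12. Entry requires a screening read of 10 or more. True anatomy does not change, and reads are independent.

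**Formula.** Only tumours truly at 9 or 10 create bias. A true 9 enters only if over-read (probability *q*, error +1). A true 10 loses its under-reads but keeps its over-reads (net +*q*). For true 11 and 12, all reads are admitted and nothing is lost. Writing P9 to P12 for the pool proportions:

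- admitted share S = q·P9 + (1 − q)·P10 + P11 + P12
- mean change = −q·(P9 + P10) / S

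Pool centred at 9: P9 = 0.261, P10 = 0.211, P11 + P12 = 0.159.
- *a* = 0.8 (q = 0.1): −0.1 × 0.472 / 0.374 = −0.13
- *a* = 0.6 (q = 0.2): −0.2 × 0.472 / 0.380 = −0.25

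Pool centred at 10.5: P9 = 0.161, P10 = 0.248, P11 + P12 = 0.500.
- *a* = 0.8: −0.1 × 0.409 / 0.739 = −0.06
- *a* = 0.6: −0.2 × 0.409 / 0.730 = −0.11

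**Share of patients with a decrease, no drug effect.** A simulation of the same model gives the same mean changes and these shares. The noise column uses a fresh baseline read that played no part in selection. There the mean change is 0.00 and decreases equal increases.

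| Pool mean, agreement | Decrease, entry read as baseline | Increase | Decrease from symmetric noise alone | Added by selection |
|---|---|---|---|---|
| 10.5, 80% | 16% | 11% | 14% | 2 points |
| 10.5, 60% | 28% | 19% | 24% | 4 points |
| 9, 80% | 22% | 11% | 16% | 6 points |
| 9, 60% | 37% | 17% | 26% | 10 points |

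With rounding and other ways of treating a misread 12, the ranges are about 14–27% from noise and 2–11 points from selection.

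**If hilar tumours enter whatever their score.** Let a fraction *h* of the pool enter that way. These patients are not selected on score and add no bias:

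- mean change = −(1 − h)·q·(P9 + P10) / [S + h·(1 − S)]
- largest: pool 9, *a* = 0.6, h = 0.3: −0.7 × 0.0944 / (0.380 + 0.3 × 0.620) = −0.0661 / 0.566 = −0.12
- smallest: pool 10.5, *a* = 0.8, h = 0.5: −0.5 × 0.0409 / (0.739 + 0.5 × 0.261) = −0.0204 / 0.870 = −0.02

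**Sensitivity.** A harsher model, in which each of the four components is misread with probability 0.05–0.20, gives −0.09 to −0.67 points, depending also on how many screened tumours score 10 or more. With a pool centred at 11 the first model gives only −0.04 to −0.08. With no reading error the bias is zero.

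**The case against.** Several objections carry weight.

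- **Size is assumed.** Neither reader agreement nor the screened distribution is in the protocol. Section 9.1 asks for the same method and technique at baseline and follow-up. If half of each reading error persisted between the two time points, the bias would halve. This stands: the direction is firm and the size is not.
- **Entry may not be cleanly truncated.** Inclusion 2 offers a hilar route that exclusion 4 closes. This stands, and the bias shrinks if that route is open.
- **The baseline may be re-read.** The protocol does not say that the entry score is carried forward unchanged, and its provision for confirming change implies looking at both scans. That is fair. But the calendar offers only one pre-treatment scan, and the confirmation is optional, confined to difficult cases and not masked to the entry score.
- **Importance.** RENAL change is secondary. Diameter and RECIST response are not themselves entry thresholds.

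Two stronger readings are tempting. One is that selection explains the whole 16–37% of patients who would show a decrease without a drug effect. It does not, because most of that is symmetric noise. The other is that selection could account for a result like the cited 71%. Even the harshest model above gives 54%. Nor does the protocol plan a comparison with that trial, whose masses also scored 10–12 and may carry a similar selection effect.

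**Conclusion.** The point holds as a minor, conditional one. Under exclusion 4, one screening scan is both the entry test and the only available baseline for the RENAL-change endpoint, and no control arm absorbs the resulting drift. Any reading error therefore biases the measured change toward reduction.

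Under 60–80% exact agreement and a pool centred at 9–10.5 (SD 1.5), the bias is about −0.06 to −0.25 points, with about 2–11 percentage points added to the share showing a decrease. If 30–50% of the pool enters by the hilar route whatever the score, it is about −0.02 to −0.12 points. All of these sizes rest on assumed inputs.

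A reader might infer that a RENAL reduction in this trial would be an artefact, or that the main result is compromised. The documents support neither. Only part of a reduction would be due to selection, and the primary objective, whether axitinib makes partial nephrectomy possible, does not use RENAL change.

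**What to change.** Use the screening RENAL score for eligibility only. After the pre-nephrectomy scan, have the same reader re-score the screening and pre-nephrectomy scans as a pair. Masking to the entry score should be required; masking to scan order should be used where feasible, which may be hard for the operating surgeon. Take RENAL change from this paired re-read, and report increases beside decreases. Inclusion 2 and exclusion 4 must also be reconciled, so that it is clear which patients were selected on the score.

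The cost is about 50 extra readings of existing scans, one per patient, with no new scan or reader. The reported reduction may be slightly smaller.

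The re-read removes the reader's error but not error fixed in the screening scan itself, such as coarse slices. If half the error is of that kind, about half the bias remains (roughly −0.03 to −0.12 instead of −0.06 to −0.25). That should be stated as a limitation.

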4.1 Axitinib Administration

Pfizer will supply Axitinib and it will be shipped in labeled boxes, with unlabeled bottles inside. The pharmacy must have labeling capabilities and fax all requests to Pfizer using the Drug Supply Request Form. Contact information is as follows:

[name], CCRC
[contact]
[contact]
[contact]

Pfizer will be provided with detailed mailing instructions, address/location of Pharmacy, Pharmacist in charge, or anything else that may be helpful for shipping.

Treatment will be administered on an outpatient basis. Axitinib will be initially dosed at 5 mg po BID with or without food. Patients tolerating axitinib at week 4 with no more than grade 2 toxicity and blood pressure controlled to $< 140/90$ mmHg (medication permitted) will have axitinib dose increased to 7mg BID. Axitinib will be dosed for a total of 8-10 weeks.

Swallow axitinib whole with a glass of water; do not split, crush, or chew. If the patient vomits

or misses a dose, an additional dose should not be taken; the next prescribed dose should be taken at the usual time

No investigational or commercial agents or therapies other than axitinib may be administered with the intent to treat the patient's malignancy.

Axitinib should be held for 1 day prior to surgery.

No axitinib will be administered after nephrectomy for any patient.

